16.1.3. Solicited and Unsolicited Adverse Events

For clinicaltrials.gov and EudraCT posting purposes, the following summary will be produced:

- The number of occurrence and the number and percentage of participants, with exact 95% CIs, of combined solicited and unsolicited non-serious adverse events (any grades, Grade 3, medically attended) during the 4-day (i.e., the day of vaccination and 3 subsequent days), 7-day (i.e., the day of vaccination and 6 subsequent days), and 30-day follow-up period (i.e., the day of vaccination and 29 subsequent days) will be tabulated by MedDRA primary SOC and PT, following each dose and overall dose and overall.
- For web posting purposes, the number of occurrences and the number and percentage of participants with non-serious AEs (solicited and unsolicited combined) during the 30-day follow-up period of any dose will be produced by SOC and PT.

- For web posting purposes, the number of occurrences and the number and percentage of participants with serious AEs, related serious adverse events, fatal serious adverse events, related fatal serious AEs during the 30 day follow up period of any dose will be produced by SOC and PT. Summary of all-cause mortality will also be presented by SOC and PT.

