
 To evaluate the safety and reactogenicity following administration of the RSVPreF3 OA investigational vaccine and PCV20, co-administered or administered alone. 	
 Percentage of participants reporting each solicited event with onset within 7 days after vaccine administration (i.e., the day of vaccination and 6 subsequent days) Percentage of participants reporting unsolicited AE within 30 days after vaccine administration (i.e., the day of vaccination and 29 subsequent days) Percentage of participants reporting SAEs after vaccine administration (Day 1) up to EoS (6 months after last vaccination) Percentage of participants reporting pIMDs after vaccine administration (Day 1) up to EoS (6 months after last vaccination)

Footnotes for the Objectives, Endpoints, and Estimands table.

Abbreviations: Ab=antibody; AE=adverse event; EoS=end of study; GMT=geometric mean titer; MGI=mean geometric increase; OA=older adult; OP=opsonophagocytic; PCV20=20-valent pneumococcal vaccine; pIMD=potential immune-mediated disease; RSV=respiratory syncytial virus; RSVPreF3 OA=respiratory syncytial virus PreFusion protein 3 older adult investigational vaccine; SAE=serious adverse event; ST=serotype.

* PCV and RSV-A endpoint will be assessed as co-primary and following the current success RSV-B will be demonstrated as sequential. Refer to [Section 9.3.1.1](#) for the testing sequence of primary objectives.

Details related to attributes of estimand covering intercurrent events, population and treatment definition are provided in the [Section 9.0](#).

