8.3.1 Time Period and Frequency for Collecting AE, SAE, and pIMD Information

All AEs (regardless of the assessment of relatedness to the study vaccines), including all SAEs and all pIMDs will be collected from the first study intervention administration. All SAEs and all pIMDs will be collected until 6 months after the last study intervention administration at the timepoints specified in the SoA ([Section 1.3](#)).

AEs (including SAEs and pIMDs) leading to withdrawal from the study will be collected from the time of the first study intervention administration until the participant is discharged from the study.

In addition, SAEs assessed as related to study participation (e.g., protocol-mandated invasive procedures) or assessed as related to any other GSK product (non-IMP) will be recorded from the time a participant consents to participate in the study until the participant is discharged from the study.

All AEs will be collected in the timeframe showed in [Table 9](#).

The investigator or designee will record and immediately report all SAEs to IQVIA via the Expedited AE Reporting Form. Reporting should, under no circumstances, occur later than 24 hours after the investigator becomes aware of an SAE, as indicated in [Appendix 3](#). The investigator will submit any updated SAE data to IQVIA within 24 hours of it being available.

Table 9 Timeframes for Collection and Reporting of Safety Information for the Co-ad Group

Event	Visit 1	Visit 1			Visit 2	Contact 1
	Day 1	Day 1	Day 7	Day 30	Day 31	Month 6**
	Pre-Dose*	RSV + PCV20 vacc				Study Conclusion
Administration site and systemic solicited events (eDiary)						
Unsolicited AEs						
All SAEs						
All pIMDs						
SAEs related to study participation or concurrent GSK medication/vaccine						
AEs/SAEs leading to withdrawal from the study						
Intercurrent medical conditions						

Abbreviations: AE=adverse event; Co-ad=co-administration; eDiary=electronic diary; pIMD=potential immune-mediated disease; SAE=serious adverse event; Vacc=vaccination.

■ shading indicates applicable timeframe for reporting of safety information.

■ shading indicates reporting timeframe applicable if solicited symptoms persist after 7 days.

*Collection of SAEs related to study participation or GSK medication/vaccines starts as of informed consent (prior to study intervention administration).

**Six months after vaccination co-administration.

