Secondary	RSVPreF3 OA and PCV20 co-administered (Co-Ad) or received separately (Control)	Adults aged \geq 60 YOA	Each Potential Immune-Medicated Disease (pIMD) event within 6 months of last dose of study intervention	1. Permanently discontinued from study due to any reasons prior to end of study	1. Missing data won't be imputed. Summaries will present the actual data	Percentage and exact 95% CIs of participants with SAEs within 6 months after last dose of study intervention (Days 1 to 6 months [i.e., 180-210] after each vaccine [i.e., date of RSVPreF3 OA vaccine administration for Control group becomes Day 1 for recording events within 6 months]).

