16. SAFETY OUTCOMES

All outputs for safety outcomes will be based on the ES.

There will be no statistical comparisons between the study intervention groups for safety data.

Secondary Safety Endpoints

- Solicited events
 - Percentage of participants reporting each solicited administration site event (pain, erythema / redness, swelling) with onset within 7 days (i.e., the day of vaccination and 6 subsequent days) following each dose and overall. Percentage of participants reporting each solicited systemic event (fever, headache, fatigue, myalgia, arthralgia) with onset within 7 days (i.e., the day of vaccination and 6 subsequent days) following each dose and overall
- Unsolicited adverse events
 - Percentage of participants reporting unsolicited AE within 30 days (i.e., the day of vaccination and 29 subsequent days) following each dose and overall
- Combined solicited and unsolicited AEs
 - Percentage of participants with combined solicited and unsolicited AEs (any grades, Grade 3, medically attended) during the 4-day (i.e., the day of vaccination and 3 subsequent days), 7-day (i.e., the day of vaccination and 6 subsequent days), and 30-day follow-up period (i.e., the day of vaccination and 29 subsequent days).
- SAEs

- Percentage of participants reporting SAEs after vaccine administration (Day 1) up to End of Study (EoS) (6 months after last vaccination)
- pIMDs
 - Percentage of participants reporting pIMDs after vaccine administration (Day 1) up to EoS (6 months after last vaccination), where pIMDs commence after vaccine administration (Day 1) and are not present prior to vaccine administration or are present prior to vaccine administration and worsened after vaccine administration (Day 1).

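### The web-posting tables of serious and fatal adverse events stop 30 days after any dose, although SAEs are collected and analysed to 6 months after the last dose

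*SAP*

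**What the plan says.** SAP 16.1.3 opens with its purpose: "For clinicaltrials.gov and EudraCT posting purposes, the following summary will be produced". Its last bullet lists tables of SAEs, related SAEs, fatal SAEs and "related fatal serious AEs during the 30 day follow up period of any dose will be produced by SOC and PT". The same bullet adds: "Summary of all-cause mortality will also be presented by SOC and PT". No window is given for that mortality summary.

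The other provisions on SAEs use a longer period:

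- Protocol 8.3.1, on collection: "All SAEs and all pIMDs will be collected until 6 months after the last study intervention administration".
- Protocol 3.0, secondary endpoint: "Percentage of participants reporting SAEs after vaccine administration (Day 1) up to EoS (6 months after last vaccination".
- SAP 16, secondary safety endpoint: "Percentage of participants reporting SAEs after vaccine administration (Day 1) up to End of Study (EoS) (6 months after last vaccination".
- SAP 16.1.4 tabulates SAEs from first vaccination to study end, repeats this for related SAEs and for fatal SAEs, and lists all SAEs.

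SAP 3.3 declares no changes to the protocol-defined analyses, and no reason is given for the shorter posting window.

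Separately, in the estimand table of SAP 2.4 the variable of the last row is pIMD events, but its population-level summary reads "Percentage and exact 95% CIs of participants with SAEs within 6 months after last dose of study intervention", the same words as in the SAE row above it.

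**The concern.** Section 16.1.3 is the only place in the SAP that marks SAE tables for public posting. Followed as written, it gives tables that leave out most of the SAE follow-up the trial collects. It also sets one 30-day window in Co-Ad, which is dosed on one day, against two such windows in Control, which is dosed on two. A reader of a registry page would see two columns of percentages with nothing to show that Control was watched for twice as long. The distortion would favour co-administration.

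The SAP does not otherwise treat 30 days as its SAE window. In the overview table of 16.1.2 the 30-day qualifier is attached to the unsolicited events and not to serious events, pIMDs or fatal serious events. In 16.1.5 demyelinating disorders are counted within 30 days, but serious ones to study end. The bullet just before the one at issue, on non-serious events, carries the same 30-day phrase, and there it matches the collection period. A carry-over from that bullet is plausible.

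**Working it through.** **Inputs**

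- Length of the window: SAP 16.1.3 defines it as the day of vaccination plus 29 days, so 1 + 29 = 30 days per dosing day.
- Dosing days: Co-Ad Day 1; Control Day 1 and Day 31 (SAP 3.1).
- Interval between the Control doses: 30 days planned, 30 to 42 allowed (Protocol 1.3, Table 4; SAP 6.4).
- Last dose to final contact: 180 days planned, 180 to 210 allowed (same tables, and Protocol Table 3 for Co-Ad).

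**Days covered**

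The Control doses are at least 30 days apart, so the two windows do not overlap: 30 + 30 = 60 days for a participant given both doses.

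| | Co-Ad | Control |
|---|---|---|
| Planned follow-up | 180 | 30 + 180 = 210 |
| Covered, planned | 30/180 = 16.7% | 60/210 = 28.6% |
| Days left out, planned | 150 | 150 |
| Longest follow-up in window | 210 | 42 + 210 = 252 |
| Covered, longest | 30/210 = 14.3% | 60/252 = 23.8% |
| Days left out, longest | 180 | 192 |

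Ratio of time at risk, Control to Co-Ad: 60/30 = 2.0 in the posting tables; 210/180 = 1.17 over full planned follow-up. These ratios need no assumption about SAE rates.

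**Illustration with a constant rate**

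The documents give no SAE rate, so the 180-day risk p is an assumption, taken as 1%, 3% or 6% and equal in both arms. With λ = −ln(1 − p)/180, the risk over t days is 1 − exp(−λt).

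| p | Co-Ad, 30 days | Control, 60 days | Control, 210 days |
|---|---|---|---|
| 1% | 0.167% | 0.334% | 1.166% |
| 3% | 0.506% | 1.010% | 3.491% |
| 6% | 1.026% | 2.041% | 6.964% |

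At p = 3% the posting tables omit 1 − 0.506/3.000 = 83.1% of Co-Ad participants with an SAE, and 1 − 1.010/3.491 = 71.1% of those in Control. Per 545 participants they show 2.8 of 16.3 in Co-Ad and 5.5 of 19.0 in Control.

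**Illustration with a raised rate after vaccination**

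Let the Co-Ad rate in its window be k times background, and count cumulative hazard in background days (close to risk when events are rare).

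- If one vaccine raises the rate by the same factor as two given together, the ratio is 60k/30k = 2.
- If each vaccine adds an equal excess without interaction, the Control rate in each window is (k + 1)/2 times background. At k = 2: 60 × 1.5 = 90 against 30 × 2 = 60, ratio 1.5. At k = 3: 60 × 2 = 120 against 30 × 3 = 90, ratio 1.33.

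So the ratio under a raised early risk depends on the model.

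**The case against.** The strongest reply is that nothing is lost from the analysis. SAP 16.1.4 already gives SAE, related-SAE and fatal-SAE tables over the full period, with a listing of every SAE; the overview table in 16.1.2 adds serious and fatal events by group. The posting tables are extra outputs, and nothing says that they replace these. This stands, and it limits the weight of the point. It does not reach related fatal SAEs, which are named as a table only in 16.1.3.

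A reader might infer that the public record will under-report SAEs. The documents do not establish that. They do not say whether the 16.1.4 tables will also be posted. What is shown is that the tables designated for posting have the wrong window.

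A reader might also infer that Control would show twice the SAEs whatever their timing. That holds for a constant, equal rate and not generally, as the additive case shows. The unequal time at risk comes from the staggered design and affects every summary taken over 30 days after any dose, including unsolicited events. The SAP also states: "There will be no statistical comparisons between the study intervention groups for safety data". For unsolicited events, however, 30 days is the collection period; for SAEs it is not. At a 3% risk the counts would be too small to show a reliable two-fold pattern.

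The 30-day phrase could be read as applying only to the last item in its list. The natural reading covers all four, and the other reading would still leave related fatal SAEs cut at 30 days.

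Finally, a reader might conclude from SAP 2.4 that pIMDs will be analysed by counting SAEs, or that the window wording in the SAE and pIMD rows drops the days after PCV20 alone. Neither follows. The variable column of the pIMD row names pIMDs, and SAP 16 and 16.1.5 define that analysis correctly. SAP 16, 16.1.4 and 16.1.5 also state the full window. The first is a copying slip in one cell; the second is not counted here as a defect.

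**Conclusion.** The point holds for the web-posting tables. Their 30-day window conflicts with the SAE endpoint and collection period in the protocol and with the SAP's own endpoint and SAE section. On the planned schedule it covers 17% of follow-up in Co-Ad and 29% in Control, leaves out 150 collected days per arm, and moves the ratio of time at risk from 1.17 to 2.0. The Control figures assume that both doses are given. The SAE percentages rest on assumed rates. The two-fold difference in percentages rests on a constant, equal rate; in the raised-risk cases tried, with k up to 3, the ratio lies between about 1.3 and 2.

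The consequence is confined to descriptive safety outputs. No primary analysis, type I error or power figure changes, and the full-period tables in 16.1.4 stand. It is still worth correcting before outputs are produced, because these are the SAE tables the SAP marks for the registries, and because they are the only named table for related fatal SAEs.

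**What to change.** In SAP 16.1.3, produce the posting tables of SAEs, related SAEs, fatal SAEs and related fatal SAEs from first vaccination (Day 1) to end of study, that is, 6 months after the last vaccination received. State the same window for the all-cause mortality summary. Showing days at risk per arm beside the percentages would help, since 180 against 210 days is still unequal, but this is optional.

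As a minor correction, replace SAEs with pIMDs in the population-level summary cell of the pIMD row in SAP 2.4.

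The cost is a few lines of SAP text and a changed date filter on data already collected. No new data, visits or participants are needed.

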16.1.4. Serious Adverse Events

Analysis of serious adverse events (SAEs) from first vaccination (Visit 1, Day 1) up to 6 months post-last vaccination, the reporting period will start at vaccination and will end at approximately 6 months post last vaccination received for Co-Ad group participants (i.e., 180-210 days post last-dose) and approximately 6 months post last vaccination received for Control group participants. SAEs will be summarized by MedDRA SOC, HLT and PT.

SAEs will be summarized and listed as:

- The number and percentage of participants, with exact 95% CIs, with at least one report of SAE with onset after each vaccine administration up to study end (i.e., 6 months post-last vaccination). This summary will be repeated for: This summary will be repeated for:
 - Considered Causally related by investigator SAEs
 - Fatal SAEs
- All SAEs will be included in a listing.
- All SAEs leading to study discontinuation or vaccine discontinuation at any point from first vaccination up to study end will be included in a listing and a tabulated listing.

16.1.5. pIMDs

For analysis of pIMDs from first vaccination (Visit 1, Day 1) up to 6 months post-last vaccination, the reporting period will start at vaccination and will end at 6 months post-last vaccination (i.e., day of last vaccination+[180-210]). pIMDs will be summarized by MedDRA SOC, HLT and PT.

pIMDs will be summarized and listed as follows:

- The number and percentage of participants, with exact 95% CIs, with at least one report of pIMD (all pIMDs, considered causally related by investigator separately) with onset after each vaccine administration up to study end (i.e., 6 months post-last vaccination) will be summarized.

- All pIMDs will also be described in detail in a listing and in a tabulated listing of pIMDs leading to discontinuation of study will be provided. Classification by new onset vs exacerbations of pIMDs will also be presented.
- The number and percentage of participants, with exact 95% CIs, with at least one report of neurological demyelinating disorder with onset within 30 days of any dose will be summarized. This summary will be repeated for serious neurological demyelinating disorder with onset after each vaccine administration up to study end.

17. DATA NOT SUMMARIZED OR PRESENTED

The other variables and / or domains not summarized or presented are:

- Physical Examination

These domains and / or variables will not be summarized or presented, but will be available in the clinical study database, SDTM and/or ADaM datasets.

APPENDIX 1. PROGRAMMING CONVENTIONS FOR OUTPUTS

IQVIA Output Conventions

Outputs will be presented according to the following:

Document Headers

All TFL is to include the following header:

Vaccine: RSVPreF3 OA (RSV OA=ADJ-019)

Study 219276 – DELIVERY DESIGNATION

where delivery designation is the name of the current delivery, e.g., DRY RUN, INTERIM ANALYSIS, FINAL ANALYSIS, etc.

Dates & Times

Depending on data available, dates and times will take the form yyyy-mm-ddThh:mm:ss.

Spelling Format

English US

Presentation of Study Intervention Groups

For outputs, intervention groups will be represented as follows and in the given order:

Study Intervention Group	For Tables and Figures	For Listings (include if different to tables)
Co-Ad	Co-Ad	Co-Ad
Control	Control	Control

Presentation of Visits

For outputs, Co-Ad group visits will be represented as follows and in that order:

Long Name (default)	Short Name
Visit 1 (Day 1)	Day 1
Visit 2 (Day 31)	Day 31

For outputs, Control group visits will be represented as follows and in that order:

Long Name (default)	Short Name
Visit 1 (Day 1)	Day 1
Visit 2 (Day 31)	Day 31
Visit 3 (Day 61)	Day 61

Listings

All listings will be ordered by the following (unless otherwise indicated in the template):

- Randomized study intervention group (or intervention received if it's a safety output), first by Co-Ad group then Control group,
- Center-participant ID,
- Date (where applicable).

DECIMAL PLACES

Decimal places for categorical data

- For percentages one decimal will be displayed
- Differences in percentages and their corresponding confidence limits will be displayed with one more decimal than the maximum number used to display the individual percentages, for example the difference between two percentages displayed with one decimal will be displayed with two decimals.

Decimal places for Demographic and baseline characteristics will be as follows:

The mean, median, and SD for continuous baseline characteristics (age) will be presented with one decimal.

Serological Summary Statistics

The number of decimals used when displaying GMTs/GMCs and their CIs is shown in the following table:

GMT/GMC value	Number of decimals
<0.1	3
≥0.1 and <10	2
≥10 and <1000	1
≥1000	0

When multiple categories of GMT/GMC values are present in the same table, the number of decimals displayed should match that of the smallest category (i.e., the one with the higher number of decimals). For example, if GMT/GMC values of <0.1 appear in the same table as values of ≥0.1 and <10, 3 decimals should be displayed for both.

GMT/GMC ratios and their confidence limits will be displayed with 2 decimals regardless of the actual values.

APPENDIX 2. PARTIAL DATE CONVENTIONS

When partially completed dates (i.e., dates missing a day and/or month) are used in calculations, the following standard rules will be applied:

- A missing day will be replaced by 15th.
- A missing day and month will be replaced by June 30th.

The following exceptions apply:

When partially completed dates (i.e., with missing day or month) are used in calculations, the following rules will be applied:

- AE start dates with missing day:
 - If the month is not the same as the vaccine dose, then the imputed start date will be the 1st of the month.
 - If the event starts in the same month as the vaccine dose, the flag indicating if the event occurred before or after vaccination (AE.AESTRTPT) will be used to complete the date. If 'after vaccination' is selected, the imputed start date will match the vaccine dose given during that month. If 'before vaccination' is selected, the imputed date will be one day before the vaccine dose given during that month.
- AE start dates with missing day and month:
 - If the year is not the same as the vaccine dose, then the imputed start date will be the 1st of January.
 - If the event starts in the same year as the vaccine dose, the flag indicating if the event occurred before or after vaccination (AE.AESTRTPT) will be used to complete the date. If 'after vaccination' is selected, the imputed start date will match the first vaccine dose given during that year. If 'before vaccination' is selected, the imputed date will be one day before the first vaccine dose given during that year.
- AE end dates with missing day: the imputed end date will be the last day of the month or the study conclusion date whichever comes first.
- AE end dates with missing day and month: the imputed end date will be the last day of the year (31st of December) or the study conclusion date whichever comes first.

All incomplete concomitant medication/vaccination start/end date will follow the rules above.

Imputed dates will NOT be presented in the listing.

AEs with any missing category details will not be replaced.

APPENDIX 3. LLOQ AND ULOQ VALUES FOR OP AB TITERS FOR MOPA AND LLOQ AND ULOQ VALUES FOR RSV-A AND RSV-B TITERS AND CONCENTRATIONS

LLOQ and ULOQ values for OP Ab Titers for MOPA

CCI

LLOQ and ULOQ values for RSV-A and RSV-B, Titers and Concentrations

CCI

CCI

PPD

CCI
